## **PROTOCOL HISTORY**

Protocol		
Version	Date Final	
2	See electronic date stamp on the final page of this document.	
1	7 February 2022	

## PROTOCOL AMENDMENT, VERSION 2: RATIONALE

Protocol GR42691 Corneal Endothelial Cells (CEC) Substudy has been amended following a health authority request to include additional description of the test product, faricimab. The inclusion criteria have also been updated to facilitate study recruitment. Changes to the protocol, along with a rationale for each change, are summarized below:

- Investigational sites have been updated from those within the United States only, to also include global sites, for recruitment purposes (Section 3.1.1).
- The inclusion criteria have been updated to include main Study GR42691 patients willing to participate in the CEC Substudy for at least 48 weeks and have at least the first CEC visit while enrolled in main Study GR42691, to support recruitment efforts (Section 4.1.1.1).
- The exclusion criteria were updated to clarify the excluded severity of Fuchs endothelial corneal dystrophy Grade < 2

- Additional description of the Sponsor-supplied dosing form of the investigational medicinal product, faricimab, has been provided for clarity (new Sections 4.2.1.1, 4.2.2, 4.2.2.2, and 4.2.3 have been added).
- Text has been added to inform investigators that if a patient's participation extends beyond the duration of the main study, faricimab will continue to be reimbursed until the patient completes the CEC Substudy for the study eye (Section 4.2.3).
- The primary Medical Monitor has been updated to Title Page, Protocol Amendment Acceptance Form, and Section 5.4.1).
- Text has been added to clarify the circumstances in which reimbursement will be provided for use in the fellow eye of anti-VEGF therapies that are licensed for ocular use (Section 4.3.1).
- Text has been added to refer investigators to the main Study GR42691 protocol for guidance for safety assessments while also informing sites that the CEC Substudy will continue adverse event reporting until patients have completed the Substudy regardless of the completion status of the main Study GR42691 (new Section 5 has been added; subsequent sections have been renumbered; Appendix 1, the Schedule of Activities has been updated to include these changes).

Additional minor changes have been made to improve clarity and consistency. Substantive new information appears in italics. This amendment represents cumulative changes to the original protocol.

#### PROTOCOL SYNOPSIS

TITLE: A CORNEAL ENDOTHELIAL CELLS SUBSTUDY IN

ASSOCIATION WITH GR42691 STUDY (AVONELLE-X): A

MULTICENTER, OPEN-LABEL EXTENSION STUDY TO

EVALUATE THE LONG-TERM SAFETY AND TOLERABILITY OF FARICIMAB IN PATIENTS WITH NEOVASCULAR AGE-RELATED

**MACULAR DEGENERATION** 

**PROTOCOL NUMBER:** GR42691 Corneal Endothelial Cells Substudy

**VERSION NUMBER:** 2

**IND NUMBER**: 119225

NCT NUMBER: NCT04777201

TEST PRODUCT: Faricimab (RO6867461)

PHASE: III (Long-term extension)

**INDICATION:** Neovascular age-related macular degeneration

**SPONSOR:** F. Hoffmann-La Roche Ltd

#### **OBJECTIVES AND ENDPOINTS**

The primary objective for this substudy is to evaluate the impact of faricimab on corneal endothelial cell health on the basis of the following endpoints, as assessed by specular microscopy:

- Primary endpoint: Percent change in corneal endothelial cell density (ECD) from baseline at Year 1 (defined as the earliest substudy visit closest to Week 52 occurring between Week 48 and Week 64) in the study eye as compared with the fellow eye
- Secondary endpoint: Percent change in corneal ECD from baseline at substudy midpoint (defined as the earliest substudy visit closest to Week 24 occurring between Week 20 and Week 28) in the study eye as compared with the fellow eye
- Exploratory endpoints:
  - Percent change in the coefficient of variation (CV) of corneal endothelial cell area (standard deviation of the cell area/mean cell area) from baseline at substudy midpoint and Year 1 in the study eye as compared with the fellow eye
  - Percent change of hexagonal endothelial cells (HEX) from baseline at substudy midpoint and Year 1 in the study eye as compared with the fellow eye

#### **STUDY DESIGN**

#### **DESCRIPTION OF STUDY**

The *main* Study GR42691 is a multicenter long-term extension study designed to evaluate the long-term safety and tolerability of intravitreal faricimab 6 mg administered at a personalized treatment interval (PTI) to patients with neovascular age-related macular degeneration (nAMD) who enrolled in and completed one of the Phase III studies, GR40306 and GR40844. Patients enrolled in GR40306 or GR40844 were randomized in a 1:1 ratio to receive faricimab at a PTI up to Q16W (experimental arm) or aflibercept Q8W (comparator arm).

This substudy is designed to evaluate the impact of intravitreal faricimab 6 mg administered at a PTI on the health of the corneal endothelial cells in patients with nAMD. Fellow eyes of enrolled patients will be used as a comparator for corneal endothelial cells analyses.

#### **NUMBER OF PATIENTS**

Approximately 135 patients with nAMD will be enrolled at approximately 50 investigational *global* sites from the *main* Study GR42691.

#### Faricimab—F. Hoffmann-La Roche Ltd

#### **TARGET POPULATION**

#### Inclusion Criteria

In addition to the inclusion criteria specified in the *main* Study GR42691 (see *main* Study GR42691 Section 4.1.1.1), patients must meet the following criteria:

- Signed Informed Consent for this substudy
- Must be able to participate for at least 48 weeks in the CEC Substudy and have at least the first CEC visit while enrolled in main Study GR42691

#### General Inclusion Criteria

Patients must meet the following ocular inclusion criterion for substudy entry:

 Difference of < 10% in ECD at screening between the two eyes as measured by specular microscopy and determined by the independent reading center

#### **Exclusion Criteria**

In addition to all criteria specified in the *main* Study GR42691 protocol, patients will be excluded from this substudy if they meet the following criteria:

#### FELLOW (NON-STUDY) EYE

- · Prior and/or current administration of faricimab
- Prior administration of brolucizumab

#### **EITHER EYE**

- Corneal ECD ≤ 1500 cells/mm² in either eye at screening as determined by the independent corneal reading center
- Fuchs endothelial corneal dystrophy Grade ≥ 2
- Previous ocular trauma (blunt or penetrating) and/or corneal endothelial cell damage, including from blunt or surgical trauma (including complicated cataract surgery resulting in complicated lens placement such as anterior chamber intraocular lens, sulcus intraocular lens, aphakia, etc.)
- Any ocular condition that precludes obtaining an analyzable specular microscopy image
- · Active or history of corneal edema
- Any active or history of corneal dystrophies, excluding Fuchs endothelial corneal dystrophy Grade <2
- Active or history of iridocorneal endothelial syndrome
- Active or history of pseudoexfoliation syndrome
- Active or history of herpetic keratitis or kerato-uveitis (including herpes simplex virus and herpes zoster virus)
- Intraocular laser therapy including selective laser trabeculoplasty, yttrium-aluminum garnet (YAG), prophylactic peripheral iridotomy within 1 year of screening, or YAG capsulotomy within 3 months of screening
- Prior vitrectomy surgery, submacular surgery, or other surgical intervention for age-related macular degeneration
- Prior pars plana vitrectomy surgery
- Previous intraocular device implantation excluding intraocular lenses
- Cataract surgery within 6 months of screening or planned for during the study
- History of glaucoma-filtering surgery, tube shunts, or microinvasive glaucoma surgery.
   Other types of prior glaucoma surgery are allowed providing that the surgery occur more than 6 months before screening
- Administration of topical Rho kinase inhibitors (e.g., Rhopressa eye drops) within 1 month prior to the screening visit
- Contact lens wear in either eye within 2 months of screening

- History of corneal transplantation, including partial-thickness corneal grafts (e.g., Descemet membrane endothelial keratoplasty, Descemet stripping endothelial keratoplasty)
- Active or history of iridocorneal endothelial syndrome
- · Active or history of pseudoexfoliation syndrome

#### **END OF SUBSTUDY**

The end of this substudy is defined as the date when the last patient, last visit occurs.

#### **LENGTH OF SUBSTUDY**

The end of the substudy is expected to occur approximately 48 weeks after the last substudy patient is enrolled.

#### **INVESTIGATIONAL MEDICINAL PRODUCTS**

#### **TEST PRODUCT (INVESTIGATIONAL DRUG)**

The investigational medicinal product(IMP) for this study is faricimab (test product). Faricimab will be supplied by the Sponsor as a sterile liquid for intravitreal injection in single-use glass vials.

Each single-use, 2 mL glass vial contains 6 mg (nominal) of faricimab formulated as 120 mg/mL in L-histidine/acetate buffer solution (approximately pH 5.5) containing sodium chloride, sucrose, L-methionine, and polysorbate 20 and is designed to provide a dose of 6 mg/0.05 mL for intravitreal injection.

#### STATISTICAL METHODS

#### **PRIMARY ANALYSIS**

The percent change in corneal ECD from baseline at Year 1 will be analyzed using the paired t-test. The 95% confidence intervals for Year 1 values as well as change-from-baseline at Year 1 will be calculated.

#### **DETERMINATION OF SAMPLE SIZE**

No formal sample size calculations were performed for this substudy. A planned enrollment of approximately 135 patients from the *main* Study GR42691 was selected in order to obtain data from at least 100 patients through Year 1 to account for patients with missing data (e.g., missed visits, lost to follow-up). ECD, CV, and HEX will be assessed in the corneal endothelium evaluable set (Modified Intent to Treat [mITT] population), which includes all patients who were treated in the study eye and for whom specular microscopic images were interpretable in both the study and fellow eye both at baseline and at the substudy midpoint and/or Year 1 evaluations.

#### **INTERIM ANALYSES**

No interim analysis is planned for this substudy.

## **LIST OF ABBREVIATIONS AND DEFINITIONS OF TERMS**

Abbreviation	Definition
AMD	age-related macular degeneration
Ang2	angiopoietin-2
BCVA	best corrected visual acuity
CEC	Corneal Endothelial Cells
CV	coefficient of variation
DME	diabetic macular edema
ECD	endothelial cell density
FDA	Food and Drug Administration
HEX	hexagonal endothelial cells
IMP	investigational medicinal product
mITT	modified intent-to-treat
nAMD	neovascular age-related macular degeneration
PTI	personalized treatment interval
Q8W	every 8 weeks
Q16W	every 16 weeks
VEGF	vascular endothelial growth factor
SD	standard deviation
YAG	yttrium-aluminum garnet

## 1. BACKGROUND

### 1.1 BACKGROUND ON FARICIMAB

See main Study GR42691 Section 1.2.

#### 1.2 BACKGROUND ON CORNEAL ENDOTHELIAL CELLS

The corneal endothelium is a single layer of cells lining the posterior portion of the cornea that regulates the health and optical transparency of the cornea (Van den Bogerd et al. 2019). The structural and functional integrity of the corneal endothelium can be impacted by a variety of extrinsic and intrinsic factors, including genetics, race, age, corneal dystrophy, ocular trauma, intraocular surgery, ultraviolet radiation, and intraocular infection. Morphological changes in the corneal endothelium occur throughout life, including a significant decline in corneal endothelial cell density (ECD) and percentage of hexagonal cells with age (Bourne et al. 1997; Zavala et al. 2013). At birth, human ECD is approximately 5000 to 6000 cells/mm^2, and gradually decreases to about 3500 cells/mm^2 by 5 years of age, 3000 cells/mm^2 by 14 to 20 years of age, and 2500 cells/mm^2 in late adulthood due to an age-related increase in the corneal cell dimensions and normal senescence of the endothelial cells (Chaurasia and Vanathi 2021). Changes in normal human corneal endothelium in adult patients were studied for over 10 years and showed a calculated rate of cell loss at approximately 0.6% per year (Bourne et al. 1997). Additional factors can influence or induce corneal endothelial cell loss as seen, for example, by the exacerbation of loss following cataract surgery. Cell loss rates up to 10 years following cataract surgery (phacoemulsification) were reported as 2.5% per year, which is four times higher than the average rate due to the aging process alone (Choi and Han 2019). The greatest corneal endothelial cell loss occurs primarily in the first 1 to 3 months following cataract surgery (Bourne et al. 1997; Beato et al. 2021) and stabilizes approximately 6 months post-operatively (Dick et al. 1996; Bourne et al. 2004; Lass et al 2019; Kelkar et al. 2020).

Specular microscopy is an imaging modality that allows for direct assessment of the corneal ECD and morphology and is routinely used in the assessment of corneal endothelial cell health (Chaurasia and Vanathi 2021). Variables studied in the specular microscopy examination include ECD, percentage of hexagonal endothelial cells (HEX), and coefficient of variation (CV) of cell area and collectively allow the clinician to interpret the health status of the corneal endothelial cells (Chaurasia and Vanathi 2021). Human corneal endothelium consists of a monolayer of hexagonal cells situated in the posterior surface of the cornea (Schmedt et al. 2012) and healthy cornea has approximately 60% of HEX (Chaurasia and Vanathi 2021). The percentage of HEX decreases (pleomorphism) and the CV of cell area increases (polymegathism) with age and endothelial cell attrition due to various causes (Chaurasia and Vanathi 2021).

Corneal ECD is an important clinical parameter that enables assessment of the risk of functional decompensation of cornea and evaluation of the functional reserve of the

corneal endothelium in individual patients. Clinical observations indicate that an ECD of about 400 to 600 cells/mm² is a threshold at which corneal decompensation develops resulting in corneal edema accompanied by loss of corneal transparency (Arici et al 2014). The most common causes for corneal endothelial decompensation include cataract surgery or intraocular lens implantation-related complications and Fuchs endothelial corneal dystrophy (Ong Tone et al 2021).

## **Angiogenic Privilege of Corneal Endothelium**

Maintenance of homeostasis between pro- and anti-angiogenic factors in the cornea regulates processes such as endothelial cell proliferation, survival, and apoptosis (Menzel-Severing 2012). In a recent literature search, no peer-reviewed literature was found showing Tie2 receptor expression on corneal endothelial cells. Tie2 receptor expression is absent on normal corneal endothelial cells, except in the instances of pathological corneal neovascularization. In this situation, Tie2 can be found expressed in the cornea only on the pathologically infiltrating vascular cells (Yan et al. 2017). Although high levels of Ang2 expression were detected in pathologically vascularized corneas, Ang2 levels in the corneal endothelial cells of normal corneas are low (Ferrari et al. 2016), and increased levels in the experimental pathological neovascularization corneal models could be reduced with anti-Ang2 treatment (Ferrari et al. 2016; Zhang et al. 2017). Under certain conditions (such as corneal injury or chemical burn, viral infection, other corneal inflammatory disorders, or surgical sutures in a predisposed high-risk corneal graft recipient), pathological triggers may tilt the balance between angiogenic and anti-angiogenic factors and lead to activation of the angiogenic cascade, resulting in neovascularization of the normally avascular cornea and overexpression of angiogenic growth receptors (Azar 2006). The majority of data on angiogenic factor expression in the cornea in the literature is related to the expression of pro-angiogenic factors and their receptors in pathologically neovascularized corneal tissue, and not in normal corneal tissue.

## Potential Corneal Endothelial Cell Interactions with Intraocular Anti-VEGF Treatment

Medications administered via the intravitreal route can be eliminated from the vitreous body through both the blood-retinal barrier and the aqueous humor outflow, thus intravitreal medication can come in contact with corneal endothelial cells (Philipp et al. 2000; Del Amo et al. 2017; Lass et al. 2018). It has been postulated that VEGF receptors expressed in the corneal endothelium are in direct contact with the aqueous humor; therefore, anti-VEGF agents may potentially impact VEGF pathway dynamics within the aqueous humor and corneal endothelium (Menzel-Severing 2012; Guzel et al. 2015).

Both in vitro and in vivo studies have set out to address the potential influence of anti-VEGF antibodies on corneal endothelial cells. For instance, in vitro analysis of human donor corneas in the presence of anti-VEGF treatment showed no cytotoxic effects on the corneal endothelium up to 4 weeks post-treatment (Merz et al. 2018).

#### Faricimab—F. Hoffmann-La Roche Ltd

Though anti-VEGF has been detected in aqueous humor following intravitreal injections (Wang et al. 2014; Celik et al. 2015; Hsu et al. 2016), a number of clinical studies have concluded that there is no substantial impact on the health of the corneal endothelium. No significant differences in corneal ECD, CV, and percent of HEX were identified in patients with neovascular age-related macular degeneration (nAMD) in comparisons preceding and either immediately following aflibercept loading doses (Atilgan et al. 2020) or after single dose of aflibercept at 1-, 3-, and 6-months follow-up (Muto and Machida 2019). Additionally, RE-VIEW was a Phase IV, open-label, single-arm study that evaluated corneal endothelial cell health by specular microscopy in eyes treated with repeated intravitreal aflibercept injection (Lass et al. 2018). Patients with nAMD received aflibercept intravitreal injections every 8 weeks (Q8W) after 3 monthly doses and had specular microscopy assessments performed at baseline and Weeks 24 and 52. RE-VIEW concluded that repeated intravitreal aflibercept injections compared to untreated fellow eyes had no significant impact on ECD, CV, and percent HEX at 1-year follow-up (Lass et al. 2018). Similarly, studies specifically using ranibizumab for intravitreal injections showed no significant impact on ECD, CV, and percentage of HEX up to 1-month (Joshi et al. 2019) and 6-months after injection (Perez-Rico et al. 2010). Conversely, a retrospective study of patients with age-related macular degeneration (AMD) receiving repeated treatments of either aflibercept or ranibizumab detected a statistically significant ECD loss from baseline up to 6-months after the first treatment (Urban et al. 2020); however, the authors noted that they had comparable measurements to multiple other studies where no statistically significant changes were detected. Collectively, safety analyses of pivotal trials for ranibizumab have detected no corneal toxicity and a majority of studies have shown that intravitreal anti-VEGF has no significant effect on the health of corneal endothelial cells.

Similarly, safety analyses from the Phase III studies GR40306 (TENAYA) and GR40844 (LUCERNE) of faricimab in patients with nAMD and from the Phase III studies GR40349 (YOSEMITE) and GR40398 (RHINE) of faricimab in patients with diabetic macular edema (DME) did not identify any clinically detectable cornea-related events that could be indicative of corneal endothelial cell toxicity, such as corneal edema; however, the direct impact of faricimab on the density of the corneal endothelium analyzed by specular microscopy has not yet been investigated.

## 1.3 SUBSTUDY RATIONALE AND BENEFIT—RISK ASSESSMENT

The four faricimab Phase III studies (GR40306 and GR40844 in patients with nAMD, and GR40349 and GR40398 in patients with DME) showed that faricimab 6 mg at intervals of up to every 16 weeks (Q16W) was non-inferior to aflibercept 2 mg Q8W for the primary endpoint of change from baseline in mean best corrected visual acuity (BCVA) at 1 year. Overall, all four studies indicated that faricimab was generally well tolerated and had a comparable safety profile to aflibercept, and a positive benefit-risk was established.

Although previous studies showed that anti-VEGF treatments do not significantly affect the health of the corneal endothelium (Benítez-Herreros et al. 2010; Perez-Rico et al. 2010; Joshi et al. 2019), the impact of faricimab, which inhibits both VEGF and Ang-2, on corneal endothelial cells has not been studied.

The aim of this substudy to *main* long-term extension Study GR42691 is to evaluate the corneal endothelial cells in the study eyes of patients with nAMD receiving faricimab to fulfill a U.S. Food and Drug Administration (FDA) post-marketing requirement. The fellow eyes of the same patients will serve as the controls, and will be permitted to receive standard of care anti-VEGF treatment (if needed).

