## 3.3.3 Rationale for Use of Patient Fellow Eye as the Comparator

Documented changes occur in the morphology, cell density, and percent hexagonal cells in the corneal endothelium due to the natural progression of aging (Bourne et al. 1997). Large inter-patient variability in corneal endothelium morphology can be due to factors such as age, gender, ethnicity, and ocular and non-ocular disorders (Carlson et al. 1988; Snellingen et al. 2001; Shi et al. 2019); therefore, comparison of corneal endothelial cells' health between two eyes of the same patient (one eye treated with faricimab, the other eye without) is appropriate to account for changes that would typically occur in a given patient.

Current evidence suggests that intravitreally administered anti-VEGF agents, as described in Section 1.2, have no negative impact on corneal endothelial health. However, safety data have shown that treatment with brolucizumab is associated with intraocular inflammation that could lead to retinal vasculitis or retinal artery occlusion. Therefore, patients who previously received brolucizumab in the fellow eye will be excluded (see Section 4.1.2) but there will be no other specific exclusion of patients who have received previous treatment in the fellow eye with other intravitreal anti-VEGF agents.

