#### 1.2 STUDY DESIGN

The main Study GR42691 (AVONELLE-X) is a multicenter long-term extension study designed to evaluate the long-term safety and tolerability of intravitreal faricimab 6 mg administered at a PTI to patients with nAMD who enrolled in and completed one of the Phase III studies, GR40306 and GR40844.

This substudy is designed to evaluate the impact of intravitreal faricimab 6 mg administered at a PTI on the health of the corneal endothelial cells in patients with nAMD. Fellow eyes of enrolled patients will be used as a comparator for corneal endothelial cell analyses. Prior and/or current administration of faricimab in the fellow eye is one of the exclusion criteria for this substudy (refer to protocol Section 4.1.2). During the substudy, the following therapies are prohibited:

- faricimab
- brolucizumab (Beovu®)
- bevacizumab (Avastin®)
- Port Delivery System implantation (Susvimo™)

Patients in the main Study GR42691 will be eligible to screen for participation in this substudy. During the substudy screening visit, eligibility to participate will be determined Faricimab—F. Hoffmann-La Roche Ltd

Statistical Analysis Plan GR42691 CEC Substudy

based on the inclusion and exclusion criteria for this substudy (refer to protocol Section 4.1). Study GR42691 patients are required to be willing to participate in the CEC substudy for at least 48 weeks and have at least their first CEC substudy visit while enrolled in the main Study GR42691.

Patients who do not meet the criteria for participation in this substudy (screen failure) may qualify for one re-screening opportunity (for a total of two screenings per patient) at the investigator's discretion. Patients are not required to re-sign the consent form if they are re-screened within 90 days after previously signing the consent form. The investigator will maintain a record of reasons for screen failure (refer to protocol Section 4.4.1).

Figure 1 presents an overview of the substudy design. A schedule of activities is provided in protocol Appendix 1.

Faricimab PTI Standard of care PRN Weeks 20 24 52 Scrn./ **D1** Study Eye: Faricimab 6 mg PTI Fellow Eye: Standard of Care PRN Substudy Midpoint Year 1 Data Collection Data Collection

Figure 1 Substudy Assessment Schema

D1=Day 1; PRN=pro renata (as needed); PTI=personalized treatment interval; Scrn=screening visit.

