## 2. STATISTICAL HYPOTHESES AND SAMPLE SIZE DETERMINATION

#### 2.1 STATISTICAL HYPOTHESES

No formal hypothesis testing is planned for this study.

The paired t-tests are planned for efficacy analyses for reference purposes and thus not considered formal. In general, the paired t-tests will compare the percent change from baseline between the study eye and fellow eye in each CEC parameter described in

Faricimab—F. Hoffmann-La Roche Ltd **Statistical Analysis Plan** GR42691 CEC Substudy

Section 4.2, Section 4.3 and Section 4.4, respectively in the specified groups. The test will be 2-sided, with the null hypothesis of no difference in percent change from baseline between the study eye and fellow eye in each patient. P-values and 95% confidence interval of the difference from the paired t-tests will be provided.

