#### 4.1 GENERAL CONSIDERATIONS

Unless specified otherwise, efficacy analyses will be performed on the modified intent-to-treat (mITT) set. Safety analyses will be performed on safety-evaluable set.

For efficacy analyses specified in Section 4.2, Section 4.3 and Section 4.4, baseline will be defined as the screening/Day 1 CEC image taken date. Midpoint will be defined as Faricimab—F. Hoffmann-La Roche Ltd

Statistical Analysis Plan GR42691 CEC Substudy

1

Clinical Study Report: faricimab - F. Hoffmann-La Roche Ltd Protocol Number: GR42691 Report Number: 1135769

the earliest analysis substudy visit closest to Week 24 occurring between Week 20 and Week 28. Year 1 will be defined as the earliest substudy visit closest to Week 52 occurring between Week 48 and Week 68.

Descriptive summaries for continuous endpoints will include number of observations, arithmetic mean, standard deviation, 95% CI for mean, median, minimum, maximum, first quartile (Q1), and third quartile (Q3). Descriptive summaries for binary/categorical endpoints will include frequency and/or percentages.

Data (from both study eye and fellow eye) collected after the fellow eye use of the prohibited therapies (listed below) will be excluded from the efficacy analysis:

- faricimab
- brolucizumab (Beovu®)
- bevacizumab (Avastin®)
- Port Delivery System implantation (Susvimo™)

Missing data will not be imputed.

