## 4.2.2 Main Analytical Approach for Primary Endpoint

Available corneal ECD values and percent change from baseline in ECD values will be summarized descriptively at baseline and at Year 1, for study and fellow eyes respectively.

In addition, the percent change in corneal ECD from baseline at Year 1 will be analyzed using the paired t-test comparing study and fellow eyes. P-value and 95% interval from the paired t-test will be provided.

Paired t-test will be performed among the subset of patients who had an interpretable baseline and Year 1 specular microscopic image in both eyes.

Paired t-test comparing study eyes and fellow eyes within each of the following subgroups will also be provided:

• Baseline age (<65,  $\ge 65$  to <75, and  $\ge 75$  years)

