## 4.8 CHANGES TO PROTOCOL-PLANNED ANALYSES

Per-protocol analysis was removed from the analysis plan as the study intends to reflect the impact of treatment in a real-world setting, where participants may or may not adhere to a clinical study protocol when taking/receiving medication.

Adverse Event analyses, which were not specified in the protocol, are currently planned in this SAP document, in order to provide a comprehensive safety summary during the substudy, in light of the fact that a patient's duration on the CEC substudy could extend beyond the duration of the main study.

Analyses by the main Phase III study treatment group in this substudy will not be conducted. This is due to the fact that the substudy consists of a single treatment group (faricimab), which differs from the Phase III study that includes a comparative group.

The subgroup analysis based on the number of faricimab injections received during the substudy has been removed. This decision is made because participants enrolled in the substudy at different timepoints during the main study and received faricimab prior to the substudy enrollment. Hence, the injection numbers received during the substudy do not accurately represent the cumulative exposure to faricimab in the patients, rendering such analysis less clinically meaningful and potentially misleading.

Subgroup analyses of primary and secondary endpoints by age are considered sufficient to understand the effect of age on efficacy, hence no further subgroup analyses are planned for exploratory endpoints.

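### The primary paired test pools fellow eyes with and without permitted anti-VEGF, and no planned analysis separates them, so any effect that treated fellow eyes share is attenuated.

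*Protocol*

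**What the plan says.** **Fellow-eye treatment.** Protocol 1.3 makes the fellow eye the control and says fellow eyes "will be permitted to receive standard of care anti-VEGF treatment (if needed". The schema in SAP 1.2 labels the control "Fellow Eye: Standard of Care PRN". For treatment before entry, Protocol 3.3.3 excludes earlier brolucizumab and then states that "there will be no other specific exclusion of patients who have received previous treatment in the fellow eye with other intravitreal anti-VEGF agents"; Protocol 4.1.2 also excludes fellow eyes that have had faricimab. Protocol 4.3.1 sets reimbursement terms for other licensed anti-VEGF agents in the fellow eye, so such use is expected.

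**Data handling.** SAP 4.1 removes data from both eyes only when "collected after the fellow eye use of the prohibited therapies (listed below) will be excluded from the efficacy analysis". The list has four entries: faricimab, brolucizumab, bevacizumab and the Port Delivery System. Data after any other anti-VEGF agent stay in.

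**Analysis.** SAP 4.2.2 defines the test set: "Paired t-test will be performed among the subset of patients who had an interpretable baseline and Year 1 specular microscopic image in both eyes". It sets no condition on fellow-eye treatment. Age is the only subgroup. SAP 4.8 removes the per-protocol analysis, the injection-count subgroup and the analyses by Phase III arm, and adds: "Subgroup analyses of primary and secondary endpoints by age are considered sufficient to understand the effect of age on efficacy". SAP 4.5.1 summarises exposure to faricimab in the study eye only.

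**Status of the test.** SAP 2.1 says: "The paired t-tests are planned for efficacy analyses for reference purposes and thus not considered formal".

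**The concern.** The objective is the impact of faricimab on the corneal endothelium. The pooled difference averages two contrasts: faricimab versus no injection, and faricimab versus another anti-VEGF agent. Where the fellow eye is treated, any effect common to both treatments cancels within the pair.

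Protocol 1.2 itself raises a shared mechanism as a possibility, saying that "anti-VEGF agents may potentially impact VEGF pathway dynamics within the aqueous humor and corneal endothelium". Protocol 3.3.3 allows treated fellow eyes because current evidence suggests that these agents do no corneal harm. That reasoning assumes the answer to part of the question being asked.

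A small pooled difference could then mean that there is no effect, or that an effect is partly shared by treated controls. No planned output separates the two by means of an untreated concurrent control, and none shows how many fellow eyes were treated. The earlier aflibercept study cited in Protocol 1.2 compared with untreated fellow eyes, so the pooled result cannot be set directly beside it.

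**Working it through.** **Is there a figure to reproduce?** No. Protocol 6.1 and SAP 2.2 state that no formal sample size calculation was done. No effect size, SD or power is given.

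**Inputs from the documents**
- Pairs: n = 100, the Year 1 target in Protocol 6.1. SAP 2.2 reports 117 enrolled.
- Scale marker: 2.5% loss per year after cataract surgery minus 0.6% per year with ageing (Protocol 1.2) = 1.9 points. It fixes a scale and is not an expected injection effect.
- Two-sided 5% level, matching the 95% CI in SAP 2.1.

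**Assumed inputs (not in the documents)**
- q, the share of fellow eyes treated with permitted anti-VEGF: 0.2 to 0.5.
- s, the share of the faricimab effect that treated fellow eyes also carry: 0, 0.5 or 1.
- SD of the paired difference in percent change: 5 to 10 points.

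**Step 1: expected pooled difference.** In a pair with an untreated fellow eye the expected difference is Δ. In a pair with a treated fellow eye it is Δ(1 − s). Averaging:

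(1 − q)Δ + qΔ(1 − s) = Δ(1 − s × q)

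With Δ = 1.9:
- s = 0 (for example an Ang-2-only effect): 1.9 at every q.
- s = 0.5: 1.9 × 0.90 = 1.71 at q = 0.2; 1.9 × 0.75 = 1.43 at q = 0.5.
- s = 1: 1.9 × 0.80 = 1.52 at q = 0.2; 1.9 × 0.50 = 0.95 at q = 0.5.

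**Step 2: power.** This uses the non-central t distribution with n − 1 degrees of freedom and non-centrality δ√n / SD. The restricted analysis keeps only pairs with an untreated fellow eye, so δ = 1.9 and n = 100(1 − q).

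| Analysis | q | s | n | δ | Power, SD 5 | Power, SD 10 |
|---|---|---|---|---|---|---|
| Pooled, undiluted | any | 0 | 100 | 1.90 | 96% | 47% |
| Pooled | 0.2 | 0.5 | 100 | 1.71 | 92% | 40% |
| Pooled | 0.5 | 0.5 | 100 | 1.43 | 81% | 29% |
| Pooled | 0.2 | 1 | 100 | 1.52 | 85% | 32% |
| Pooled | 0.5 | 1 | 100 | 0.95 | 47% | 16% |
| Untreated fellow eyes only | 0.2 | any | 80 | 1.90 | 92% | 39% |
| Untreated fellow eyes only | 0.5 | any | 50 | 1.90 | 75% | 26% |

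If the effect is fully shared, the restricted analysis has more power than the pooled one (75% against 47% at q = 0.5, SD 5). If it is half shared, the restricted analysis has about equal or lower power (75% against 81% in the same cell). The case for the split is therefore that its estimate is not diluted, not that it gains power.

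**Step 3: precision of a split.** The 95% CI half-width is t(0.975, n − 1) × SD / √n.
- n = 100: 1.984 × 5 / 10 = 0.99 with SD 5; 1.98 with SD 10.
- n = 50: 2.010 × 5 / 7.071 = 1.42; 2.84.
- n = 20: 2.093 × 5 / 4.472 = 2.34; 4.68.

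**The case against.** **The contrast is deliberate and disclosed.** The schema names the control as standard of care, and the regulatory requirement quoted in SAP 1 asks for a controlled trial, not an untreated control. This stands, and it is why the pooled test should remain primary. It does not supply an analysis that shows the two components.

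**A shared effect is unproven.** Protocol 1.2 presents the VEGF mechanism as postulated, reports no toxicity in donor corneas, and says most studies found no effect. It also cites one retrospective study with significant cell loss under aflibercept or ranibizumab, with a caveat. The attenuation is therefore conditional. The split would help to examine the assumption.

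**By-eye summaries show undiluted study-eye change.** SAP 4.1 and 4.2.2 give that change with a 95% CI, and it can be read against about 0.6% loss per year. This is the strongest point: a sizeable shared loss would show there. But 0.6% is an external benchmark, and Protocol 3.3.3 justifies within-patient comparison by the large variability between patients.

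**The magnitude is assumed and the tests are informal.** Both are true. At q = 0.1 and full sharing, only 10% of the effect is lost. Because the tests are informal, interpretation rests on the estimate and CI, so what they estimate needs to be clear.

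**The split is not clean.** Groups formed by treatment given as needed after baseline are not random. SAP 4.8 also notes that patients had faricimab before substudy entry, which limits the pooled and the split results alike. This is why the split should be descriptive only.

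**Main-study outputs may already tabulate fellow-eye injections.** They may; those documents were not available. Such a table alone would not split the paired ECD result.

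**Conclusion.** The concern holds. The pooled paired difference estimates faricimab versus standard of care as needed, and nothing in the SAP shows the share of fellow eyes treated or isolates an untreated concurrent control. The primary analysis need not be replaced; the gap is in interpreting its estimate and CI.

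The size depends on q, s and the SD, none of which the documents give. Within the assumed ranges, a shared effect loses between 10% (q = 0.2, half shared) and 50% (q = 0.5, fully shared) of its size. A faricimab-only effect loses nothing. The absence of the split is certain; its consequence is conditional on a shared effect. The sponsor should make the change.

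**What to change.** 1. Keep the pooled paired t-test as primary. In SAP 4.2.2 and in the report, label it as faricimab versus standard of care as needed.
2. Add to SAP 4.2.2 a prespecified, descriptive, supportive analysis: the paired difference in percent change in ECD at Year 1 with its 95% CI, shown separately for pairs whose fellow eye received no intravitreal anti-VEGF from substudy baseline to the Year 1 image and for pairs whose fellow eye received any.
3. Add a sensitivity version of the first group that also requires no fellow-eye anti-VEGF before baseline.
4. Tabulate fellow-eye intravitreal injections by agent, before and during the substudy.

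**Cost.** SAP wording, one supportive table and one exposure table. The exclusion rule in SAP 4.1 already needs the agent and date of fellow-eye treatment, at least for the prohibited therapies. The drawbacks are wider intervals, especially if a group is as small as 20 pairs, and non-random groups that cannot replace the pooled result. The report should state both.
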